### 11.2 Sample Size:

600

### 11.3 Total number of subjects requested (including records and specimens):

600

### 11.4 If you are recruiting by study arm, please identify the arms of the study and how many subjects will be enrolled in each arm

300 in the pre-training arm (control arm)  
300 in the post-training arm (intervention arm)

### 11.5 Please provide a justification for your sample size

In order to achieve a statistical power of greater than 80% at an effect size of 0.3, we require a minimum of 200 participants to complete all follow-up in each cohort of the study, as detailed in the power analysis in Section 11.6. In order to account for a roughly 30% rate of attrition, we are requesting a sample size of 300 participants per arm, for a total of 600. Based on previous longitudinal studies by team members [name], [name], and [name], we believe that this is a conservative estimate considering the duration of each participant's involvement.

## 11.6 Data Analysis Plan: Complete description: Background, Objectives, Design, Step by Step how the project is going to be done, Data analysis plan:

In order to assess for significant differences between two cohorts of patients, bivariate comparisons will first be conducted using a Chi-squared (Fisher exact) test to compare proportions of categorical (dichotomous outcomes) and an unpaired t-test for mean changes of continuous outcomes (i.e. Pain Disability Index scale, self-efficacy, positive outcome expectation, catastrophizing, fear avoidance beliefs and distress).

Alternatively, Wilcoxon nonparametric counterpart will be used for continuous variables where there is deviation from normality. These univariate analyses will be followed by multivariable regression methods for an adjustment of all other potential confounding variables. We will also use longitudinal logistic models (i.e., mixed-effects regression models with a random subject effect and GEE with exchangeable and independent correlations) to analyze the changes of the outcome at baseline at all follow-up times (baseline, post-treatment, at 6 months, and 1 year). Psychological outcomes will be analyzed at baseline and at post-treatment (approximately 4 weeks of enrollment). The models will be specified with random intercepts and slopes such that a linear trajectory representing outcomes will be compared between two arms. For example, longitudinal changes in all available continuous psychological outcomes over time of follow-up will be displayed using locally weighted smoothing scatter (lowess) plots, identifying nonparametric mean trajectories over time. Mean trajectories then will be modeled with mixed-effects linear regression models, and if necessary using segment-linear models to approximate non-linear mean trajectories for ease of interpretation. Group (arm)-specific (as well as individual-level) intercepts and slopes over the period of follow-up will be included as random effects, while other covariates such as other clinical or demographic confounders will be modeled as fixed effects. An interaction term will be also assessed to test group differences in outcomes over time. Residual-based diagnostics will be used to evaluate validity of model assumptions. Two sided p-values <0.05 will be considered to be statistically significant. All statistical procedures will be performed using R statistical package ([www.R-project.org](http://www.R-project.org)).

In order to determine the association of treatment effects among the subjects who endorse the mental care questions, we will further perform the sub-analysis using the regression analysis similarly stated as above. All covariates and their source are shown in the tables of variables found in Section 10.2. This analytic approach will be hypotheses generating and will be largely exploratory as the study may not be powered to detect significant effects. Therefore, we have not proposed any formal power calculation for the sub-analysis.

Assuming normality, we calculated the statistical power for various detectable effect sizes and sample sizes in a two-sided hypothesis test with a significance level of 0.05, where the ratio of sample size of 1:1 is assumed between cases (intervention arm) vs. controls. When outcomes are proportions, we calculated power based on rate differences. Table 2 shows that our sample size will have adequate power to detect listed effect sizes. For example, we will achieve 95.4% power to detect a difference of rate of 0.3 (i.e., achieving minimal clinically important difference of 80% in receiving therapy by PT staff "after training" group vs. 50% in receiving therapy by PT staff before training) between two arms of a size of 100 (117) for each with 30 (40) % of missingness. For continuous outcomes, the same size of n=100 (117) for each will have a 83.6% power to detect standardized mean difference of 0.5, which corresponds that the reduction in PDI (Pain Disability Index) score from baseline to follow-up would be 50% greater in the training group as compared to that before training. Note that for each domain outcome, the power is the same for each effect size since they are standardized, but the mean change corresponding to a given effect size differs.

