In one recent larger study, Overmeer et al developed an eight-day training course for physical therapists in PiPT including questionnaire administration, the biopsychosocial model, yellow flags, behavioral principles, communication, addressing fear of movement, and role playing. In a randomized clinical trial (RCT) examining the effectiveness of this training, the investigators found that while attitudes and knowledge of the physical therapists shifted in the expected direction, their behavior did not. Furthermore, training did not improve patient outcomes. However, patients with high levels of catastrophizing and depression showed better outcome regarding disability when the attitudes of therapists changed from purely biomedical to psychologically-based. The authors point out that a one-time course is insufficient for changing behaviors, even if attitudes are altered. Ongoing education and reinforcement is needed. This sentiment is echoed in a study by Nielsen et al. (2014), where trained physical therapists stated a preference for more role-play experience prior to implementing treatment. Secondly, Overmeer et al. (2011) speculate that their topics were too broad and did not focus on specific ways to address yellow flags. Finally, they posit a possible selection bias in that participants were interested in learning about yellow flags, so they may have already been exhibiting different behaviors than other physical therapists.

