## Phase II

### Recruitment and Consenting

- Recruitment for Phase II will largely proceed as with Phase I (pending unforeseen changes in the PT department's process). The only major change is that when researchers screen the schedule for evaluation appointments, they will also verify that the corresponding therapist completed the PiPT training.
- Research staff will brief the patient on the study.
- If the patient is interested, the researcher will show them to the private study room, screen them for eligibility, and then ask them to review the consent form. The researcher will remain in the room to answer any questions.

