### **13.3 Please describe the pre-screening process. If no pre-screening, enter Not Applicable in the text editor**

Physical therapy staff will be informed of the inclusion and exclusion criteria for our study. Researchers will use printouts of the clinic schedule received from the clinic manager to determine which patients are coming in for evaluation. In Phase II, we will also use the schedule to verify that the patient's therapist has completed PiPT training. We will let staff members conducting evaluations know that we are interested in approaching their patients after the evaluation if they are eligible. If the staff member assents, we will brief the patient on the study and ask them to verify that they are:

1. An active duty service member beginning physical therapy for their current musculoskeletal injury
2. NOT pregnant, receiving PT for post-surgical follow-up, or scheduled for or subject to a Physical Evaluation Board.

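### Training is given to therapists, but the planned tests and models name no therapist effect; their standard errors are too small if therapist mix, caseloads or effects differ between phases

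*Combined protocol and SAP*

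**What the plan says.** Section 10.1 trains the physical therapy staff between two sequential cohorts. In Phase II, when research staff screen the schedule, "they will also verify that the corresponding therapist completed the PiPT training"; Section 13.3 repeats the check. The intervention therefore acts on therapists, and each therapist sees several patients.

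Section 11.6 compares patients: chi-squared or Fisher tests, an unpaired t-test or Wilcoxon test, multivariable regression, then "mixed-effects regression models with a random subject effect and GEE with exchangeable and independent correlations". That phrase sits in a sentence on repeated measurements, so the correlation structures are naturally read as within-patient. On random effects the section adds: "Group (arm)-specific (as well as individual-level) intercepts and slopes over the period of follow-up will be included as random effects". No therapist random effect, cluster or therapist-robust variance appears.

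The power paragraph in Section 11.6 begins: "Assuming normality, we calculated the statistical power for various detectable effect sizes and sample sizes in a two-sided hypothesis test". It does not mention therapists. Section 11.5 states: "we require a minimum of 200 participants to complete all follow-up in each cohort of the study".

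Two places touch on therapist. In its sub-analysis paragraph, Section 11.6 says: "All covariates and their source are shown in the tables of variables found in Section 10.2"; those tables include therapist name. Section 10.1 promises a confounding check for therapists with previous PiPT experience.

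**The concern.** Patients of one therapist may have correlated outcomes. If so, the difference between cohorts carries a therapist component that a patient-level test ignores. In this before-and-after design, a therapist who treats similar shares in both phases and has a stable effect contributes equally to each side, and that part cancels. What does not cancel is change: staff leaving or joining, caseloads shifting, or a therapist's results drifting.

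Aim 3 rests on the between-cohort comparison at two-sided p<0.05. If therapists change in these ways, that test rejects too often when training does nothing, and a change in who treated whom can look like a training effect. The plan estimates neither therapist nor therapist-by-phase variation, so it could not show whether this had happened.

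The documents leave room for change without showing it. The training-completion check restricts therapists in Phase II only. In an earlier randomised trial of therapist training cited in Section 9.2, some patients "showed better outcome regarding disability when the attitudes of therapists changed from purely biomedical to psychologically-based". The same account says that training did not improve patient outcomes overall. It is therefore evidence that the therapist matters, not evidence of drift.

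**Working it through.** **The plan's own figure.** Inputs: standardised difference 0.3, two-sided alpha 0.05, 286 per cohort with 30% loss (Table 2), so 286 × 0.7 ≈ 200 completers per arm. A two-sample t-test with independent patients gives 84.9%, as stated. The 83.6% row reproduces in the same way (100 × 0.7 = 70 per arm, difference 0.5). The figure thus holds no allowance for therapist clustering.

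**Assumed inputs.** The documents give no ICC, therapist count, caseload or turnover. Let K be therapists per phase, m = n/K completers per therapist per phase, and r the correlation of a therapist's effect between phases (r = 0 also stands for full turnover).

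**Formulas.**
- Design effect: DE = 1 + (m − 1)·ICC − m·ICC·r. It equals 1 when r = 1 − 1/m, whatever the ICC. With n = 200 that is 0.95, 0.90 and 0.80 for 10, 20 and 40 therapists; the unclustered test is liberal only below that value.
- Type I error of the unclustered test: 2·[1 − Φ(1.96/√DE)].
- Cluster-adjusted power: two-sided t-test at 0.3 with n/DE per arm, before any degrees-of-freedom (df) correction.

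Example, K = 20, m = 10, ICC 0.05, r = 0.5: DE = 1 + 9 × 0.05 − 10 × 0.05 × 0.5 = 1.20; type I error = 2·[1 − Φ(1.96/1.095)] = 7.4%.

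**Results for the two-sample comparison, n = 200 per arm, at r = 1.0 / 0.8 / 0.5 / 0.**

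| Case | DE | Type I error, % | Cluster-adjusted power, % |
|---|---|---|---|
| K=20, ICC 0.05 | 0.95 / 1.05 / 1.20 / 1.45 | 4.4 / 5.6 / 7.4 / 10.4 | 86.7 / 83.2 / 78.0 / 69.9 |
| K=20, ICC 0.02 | 0.98 / 1.02 / 1.08 / 1.18 | 4.8 / 5.2 / 5.9 / 7.1 | 85.6 / 84.2 / 82.1 / 78.6 |
| K=40, ICC 0.05 | 0.95 / 1.00 / 1.075 / 1.20 | 4.4 / 5.0 / 5.9 / 7.4 | 86.7 / 84.9 / 82.3 / 78.0 |
| K=10, ICC 0.05 | 0.95 / 1.15 / 1.45 / 1.95 | 4.4 / 6.8 / 10.4 / 16.0 | 86.7 / 79.7 / 69.9 / 57.1 |

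Simulation of the first row (40,000 null runs per case) gave type I error of 4.2 / 5.6 / 7.2 / 10.3%. In that row the unclustered test itself still rejects in 85.7 / 84.5 / 82.9 / 80.6% of trials at 0.3 SD, so the harm is false positives rather than missed effects.

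**Caseload shift with fully stable effects.** Here DE = (1 − ICC) + ICC·(n/2)·Σ(w1 − w2)², where w1 and w2 are a therapist's shares of the two cohorts. As an illustration, take K = 20, ICC 0.05, with half the therapists going from 15 completers to 5 and half the reverse. Then Σ = 20 × (10/200)² = 0.05 and DE = 0.95 + 0.05 × 100 × 0.05 = 1.20, again 7.4%. The same staff staying on is not enough; their shares must also be similar.

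**Therapist as a fixed covariate only.** With K = 20 and ICC 0.05, let t = ICC·(1 − r). The ratio of true to estimated variance is [(1 − ICC) + m·t] / [(1 − ICC) + t·m(K − 1)/(2Km − K − 1)] = 1.00 / 1.10 / 1.25 at r = 1.0 / 0.8 / 0.5. Type I error is 5.0 / 6.2 / 7.9%.

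**Power at the expected number of completers.** 300 enrolled with 30% loss gives 210. With K = 20, ICC 0.05, r = 0.8: DE = 1 + 9.5 × 0.05 − 10.5 × 0.05 × 0.8 = 1.055, and cluster-adjusted power is 84.7%. With 19 df, the most conservative choice, power is 79.3% at 200 and 81.0% at 210.

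**The case against.** The strongest reply is that nothing here is shown to go wrong. No turnover is reported. Both cohorts come from one facility and its branch clinics, so continuing staff is plausible. Section 10.1 limits uneven delivery through an 85% pass mark, case-study evaluation, a Phase II start that waits for proficiency, and repeated reinforcement. With 20 therapists, ICC 0.05 and correlation 0.8, type I error is 5.6%; with 40 therapists it is 5.0%. All of this stands, and it limits the size of the point. It does not fill the gap in the analysis text.

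A second reply is that therapist name is in the Section 10.2 tables, to which Section 11.6 sends the reader for covariates. That sentence belongs to the sub-analysis, and nothing assigns therapist to a model. A fixed therapist effect would in any case miss change between phases. Residual diagnostics are planned, but not by therapist.

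A reader might infer more than the documents support:
- *That the standard errors are too small whatever happens.* With stable effects and similar caseload shares they are slightly too large (4.4%).
- *That uneven uptake of training inflates type I error.* If training affects no therapist's patients, uneven uptake changes nothing. It matters only for inference on the average effect across therapists.
- *That the study is underpowered.* At correlation 0.8 with 20 therapists, the expected 210 completers give 84.7%, or 81.0% with 19 df. The margin does fail at correlation 0.5 (79.5%, or 75.4% with 19 df).
- *That the figures describe the trajectory models.* They are for the two-sample comparison. In an arm-by-time interaction a constant therapist effect on outcome level cancels, and only therapist variation in change matters; its size is not computed here.

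**Conclusion.** The point holds in conditional form. The tests and models in Section 11.6 leave out the level at which training is delivered, and the 84.9% assumes independent patients. Standard errors are sound or slightly conservative with continuing therapists, similar caseload shares and stable effects. They are too small if mix, shares or effects differ between phases. Under a strict null of no training effect on any therapist's patients, the causes would be turnover, caseload shift or other drift in performance.

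The size runs from nil (40 therapists, correlation 0.8) to type I error of 10.4% (10 therapists at correlation 0.5, or 20 with full turnover) and 16.0% (10 with full turnover), all at ICC 0.05. These rest on assumed ICC, therapist count and correlation and, in the table, on equal caseloads. The omission is certain; its consequence is not. It should be fixed, with medium confidence in how much it matters.

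**What to change.** 1. Add therapist and therapist-by-phase random effects to the between-cohort outcome models (for trajectories, to the slopes as well), or cluster on therapist, with a small-sample correction. Base inference on these models and keep the unclustered tests as descriptive. Define the therapist variable as the evaluating or main treating therapist, because the documents do not say that one therapist delivers all sessions.
2. Report the number of therapists and of patients per therapist in each phase. Prespecify a sensitivity analysis limited to therapists who treat in both phases.
3. State that 84.9% assumes no therapist clustering. Show cluster-adjusted power over a range of ICC and between-phase correlation, at 200 and 210 completers per arm.

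**Limit.** This corrects the standard errors. A change common to all therapists coincides with phase, and no random effect removes it.

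**Cost.** SAP wording and some extra analysis, with no new data item. Therapist name is already on the intake form, but obtaining it depends on the data sharing agreement (Sections 10.2 and 10.14). A coded therapist ID must be in the de-identified file sent to the collaborators. Intervals will usually be wider. At ICC 0.05, correlation 0.8 and 200 completers per arm, the small-sample correction (df = therapists − 1) costs about 2 points of power with 40 therapists (84.9% to 83.3%), 4 with 20 (83.2% to 79.3%) and 9 with 10 (79.7% to 70.3%).

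### Section 11.6 tests the same between-cohort comparison with unadjusted, adjusted and longitudinal analyses, all at p<0.05, and names none of them as deciding Aim 3

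*Combined protocol and SAP*

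**What the plan says.** Section 11.6 sets out the analyses in sequence.

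- **Unadjusted.** Unpaired t-test on mean change for continuous outcomes (Wilcoxon if not normal); chi-squared or Fisher exact for categorical outcomes. The visit is not stated.
- **Adjusted.** "These univariate analyses will be followed by multivariable regression methods for an adjustment of all other potential confounding variables".
- **Longitudinal, introduced as logistic.** "mixed-effects regression models with a random subject effect and GEE with exchangeable and independent correlations", over baseline, post-treatment, 6 months and 1 year.
- **Longitudinal, continuous.** Linear mixed models with random intercepts and slopes and a test of the arm-by-time interaction. After lowess plots of the data the form may change: "if necessary using segment-linear models to approximate non-linear mean trajectories for ease of interpretation".

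The significance rule is common to all: "Two sided p-values <0.05 will be considered to be statistically significant". Only the mental-care sub-analysis is labelled exploratory. No section names a primary outcome, analysis or time point, or a rule for conflicting results.

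Section 11.6 also limits psychological outcomes to baseline and post-treatment (about 4 weeks), then describes modelling their trajectories over follow-up. Section 10.1 (Phase II, Treatment) says the sponsor expects the cohorts to differ by the 4th treatment visit. The power calculation in 11.6 and Table 2 uses the unpaired t-test and the Fisher exact test.

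**The concern.** Aim 3 (Section 9.3) is to demonstrate the effectiveness of PiPT. If several tests of that claim are each read at 5% and any may be cited, the 5% error rate does not hold even for one outcome. This problem is separate from the number of outcomes.

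The tests also ask different questions. A test of change at one visit looks for a difference that is present then. A straight-line slope over 12 months looks for cohorts that keep diverging. An early, lasting benefit suits the first and is partly missed by the second, so two analysts who both follow the plan could report opposite conclusions.

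The cohorts are sequential and not randomised, so adjusted and unadjusted answers may differ for substantive reasons. The only analyses with a power statement are the unadjusted ones, which give no protection against differences between the cohorts.

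**Working it through.** **Inputs from the documents.** Two-sided alpha 0.05; 1:1 cohorts; 300 enrolled per arm (11.4); 200 completers per arm (11.5); about 30% loss; effect size 0.3; visits at baseline, about 4 weeks, 6 and 12 months, taken as t = 0, 1, 6, 12 months.

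**Assumed, not in the documents.** Within-person correlation ρ = 0.3-0.7; no difference between cohorts other than treatment; any dropout at random. Steps 2-4 also take complete data and equal correlation between all visits.

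**Step 1: the plan's figure.** 286 × 0.70 = 200 completers per arm. Noncentrality = 0.3 / √(2/200) = 3.0 with 398 df, so power is 84.9%. Table 2 reproduces, for the unadjusted t-test only.

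**Step 2: overlap of the change and slope tests.** Change at first follow-up uses weights c = (-1, 1, 0, 0). With mean time 4.75, the slope uses s = (-4.75, -3.75, 1.25, 7.25), and Σs² = 22.5625 + 14.0625 + 1.5625 + 52.5625 = 90.75. The correlation of the two statistics is c·s / (|c||s|) = 1.0 / (1.414 × 9.526) = 0.074, whatever ρ is. They are almost independent, so the chance that at least one is significant under the null is 9.7% (full independence: 1 - 0.95² = 9.75%).

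**Step 3: add the baseline-adjusted regression at first follow-up.** Its correlation with the change test is √((1+ρ)/2). Its correlation with the slope is (4.75ρ - 3.75) / √(90.75(1+ρ)).

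| ρ | with change | with slope | two visits: change or adjusted | four visits: change, adjusted or slope |
|---|---|---|---|---|
| 0.3 | 0.806 | -0.214 | 7.7% | 12.2% |
| 0.5 | 0.866 | -0.118 | 7.3% | 11.9% |
| 0.7 | 0.922 | -0.034 | 6.8% | 11.4% |

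With two visits and complete data, the mixed-model interaction is the change test, so it adds nothing.

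Simulation (3,000 null trials per scenario, 300 per arm, ρ 0.3-0.7, 0 or 30% dropout, covariates explaining 0-30% of variance) gave a wider range:

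- Two visits: about 6-10%.
- Four visits, t-test, regression and mixed model: 12-13%.
- Four visits with two-segment slopes and the two GEE fits also counted: 15-17%. The GEE fits contribute only about 0-2 points of this.
- Each test alone: roughly 4-7%.

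**Step 4: a true effect that appears early and persists.** Let the shift be δ at each follow-up, equal to 0.3 SD of change, so δ = 0.3σ√(2(1-ρ)), with 200 per arm.

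- Change test: noncentrality 3.0, power 85%.
- Fitted slope: δ × 4.75/90.75 = 0.0523δ per month, or 0.63δ over 12 months. Noncentrality = 0.3 × √2 × (4.75/9.526) × √(200/2) = 2.115. Power = Φ(2.115 - 1.960) = 56%.
- The change test is significant and the slope is not in 37% of trials. The two disagree in 44%, and the three analyses in 49-51%.

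Other assumption sets for the same effect gave 47-57% power for the slope and 49-57% disagreement among the three. With a smaller shift of 0.2 SD at every follow-up, simulated power was 58% (change), 75% (baseline-adjusted) and 29% (slope), with 67% disagreement.

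**The case against.** **The sequence implies a hierarchy.** Bivariate tests come first and adjusted models follow, which reads as screening, then adjustment. This is a fair reading of intent, but no sentence gives the adjusted result precedence. It also would not choose between adjusted regression, linear slope and segmented slope.

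**The study is an observational hybrid type 3 design with feasibility as Aim 1.** True, and it lowers the stakes. Aim 3 still sets out to demonstrate effectiveness, and the p<0.05 rule is not restricted.

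**Different estimands are not repeated tests of one hypothesis.** Correct: the slope models use all visits and do not re-test one visit. The inflation arises because any of them could be cited for the same effectiveness claim.

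**Stronger readings that do not hold.** A reader might infer that every outcome receives a t-test, a regression, a mixed model and two GEEs. The GEEs are introduced under longitudinal logistic models and the t-test under continuous outcomes. One scale would get both sets only if it were also dichotomised, which Section 11.1 permits and Table 2's proportion above the MID suggests, but which is not stated for any named outcome.

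A reader might also put the error rate near 20%. That requires always testing segment slopes, which the plan makes conditional, or testing every follow-up separately, which it does not specify.

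Finally, the sentence limiting psychological outcomes to two time points, if it governs, removes the change-versus-slope conflict for them and leaves the 6-10% range. The later wording on trajectories makes this uncertain.

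**Conclusion.** The concern stands in this form: several analyses of the same between-cohort comparison share one 5% rule, and none is named as deciding Aim 3. For a single null continuous outcome, the chance of at least one significant result is roughly 6-10% with two time points and roughly 10-17% over four visits. The top of that range needs the segmented models.

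These values depend on the assumed correlations, dropout at random and no cohort confounding. They show an order of magnitude and are not a property that can be read off the plan. The dichotomous set has the same structure but was not quantified separately.

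The possibility of conflicting answers is firmer than any one percentage. Under an early, persistent effect the straight line recovers about 0.63 of the 12-month difference, so the change and slope tests will often disagree. How often depends on the size and shape of the effect. The 84.9% power says nothing about the adjusted or longitudinal analyses.

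**What to change.** Before analysis, add to Section 11.6:

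- **Continuous outcomes:** the deciding analysis is a covariate- and baseline-adjusted longitudinal model with visit as a categorical factor and an arm-by-visit term, read as the arm contrast at one visit that the sponsor designates.
- **Dichotomous outcomes:** the adjusted logistic equivalent, at the same designated visit.
- **Everything else:** the unadjusted tests, linear-slope and segmented models, and alternative GEE fits are sensitivity or descriptive analyses and cannot by themselves support an effectiveness claim.
- **Psychological outcomes:** state whether they are analysed at two time points or over all four.
- **Power:** say that Table 2 refers to the unadjusted tests.

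Naming any single model, contrast and visit would restore about 5% for one outcome, provided the cohorts are comparable. The adjusted visit-specific contrast is preferred because the cohorts are not randomised and because it does not force an early effect onto a straight line.

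The cost is a few sentences and no new data. The sponsor gives up some freedom over which model to cite.
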